- Scheduled for elective inpatient genitourinary surgical procedure
- Caudal anesthesia within standard of care for surgical procedure
- Have provided parental consent and assent in accordance with the Institutional Review Board requirements

Exclusion Criteria

- Abnormal/difficult anatomy
- Known allergy to ropivacaine or dexamethasone
- History of documented chronic pain
- Existing infection at site of intended injection

Enrollment:

All patients will be enrolled in the study the day of surgery, in area private hospital setting. Subjects/subject parents may be approached to consent either before or after surgery, provided all inclusion criteria is met and no exclusion criteria. The study will be explained by a member of the research team with extensive knowledge of the protocol. All medications and techniques utilized for this study are commonly accepted for routine care for these patients.

Study Procedures:

1. Study design: prospective data collection.
2. Comparison Groups: We will collect data on 94 subjects having a GU procedure and caudal as standard of care. We will collect information on 47 subjects who receive caudal only. We will collect information on an additional 47 subjects who receive a caudal and IV dexamethasone. No other adjuvant medication will be used.
3. Study and timeline of interventions
 - a. Preoperative: Patients enrolled in this study may receive 0.5mg/kg up to 15mg total of oral midazolam if deemed necessary for anxiolysis by operating room or study anesthesiologist, 15 to 30 minutes prior to anesthetic induction.
 - b. Intraoperative: Subjects will undergo induction of anesthesia by inhalation of sevoflurane and oxygen. An intravenous catheter (IV) will be placed, followed by 2-3mg/kg of propofol if necessary. The airway device (LMA or ETT) will then be placed. Following confirmation of airway placement, the patient will be rolled in left or right lateral decubitus position and caudal epidural will be placed under sterile conditions. To be enrolled as caudal + IV dexamethasone, subjects must receive IV dexamethasone right after caudal placement. Should the IV dexamethasone be given at the end of the surgical procedure, subject will be considered a screen failure. All patients will be maintained on sevoflurane in accordance to patient anesthetic requirements as determined by anesthesia provider.

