 - c. Postoperative: All patients will receive routine PACU care. Pain and anxiety scores will be recorded according to routine PACU practice. All patients will have their pain orders written by the anesthesia acute pain service and pain scores monitored per hospital protocol. The patient will have a final pain evaluation by the Acute Pain Service attending the day following caudal placement.
 - d. Measured end-points:
 - i. Type of procedure
 - ii. Time of caudal
 - iii. Length of surgical procedure
 - iv. Time to first analgesic dose
 - v. Amount of pain medicine received in PACU
 - vi. Amount of pain medicine received during floor stay
 - vii. Pain scores over 24 hour period as obtained by floor nurse during routine care

- viii. Patient/parent satisfaction
- ix. Highest pain level in 24 hour period
- x. Adverse events

Risks to patient/ adverse event response:

Per inclusion criteria, patients enrolled in this study will be receiving anesthesia, surgery, and a caudal as standard of care. IV dexamethasone will be given at the discretion of the anesthesiologist. Risks related to the study are limited to potential loss of confidentiality.

Subject Withdrawal:

A patient may withdraw from enrollment at any time. At the time of withdrawing, data already collected will be kept and utilized, but no more data for the study will be collected.

Statistical Considerations:

A two tailed paired t-test will be utilized to evaluate a clinically significant difference of 2 hours between the two groups. Each group will contain 47 participants in order to achieve a power of 0.9 and Alpha of 0.05.

Privacy/Confidentiality:

Participant privacy is an important goal of the researchers. Only the principal investigator and IRB approved study personnel will have access to identifiable data. PHI will be stored in the locked Anesthesiology Offices.

Follow up/Record Retention:

The participation in the study begins with induction of anesthesia and ends after the 24 hour follow up. The patient data related to the study will be passed on to the principal and co-investigators, and the anesthetic record will be placed in the patient's medical chart. Data will be entered and stored securely in a REDCap database. Following completion of the study and after the require amount of time per Indiana Laws, all copies of data collected will be physically destroyed.

References:

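### The only named test is a paired t-test, but the two groups are different children with no pairing rule, so the p-value depends on row order; separately, the stated power has no SD behind it

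*Combined protocol and SAP*

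**What the plan says.** Statistical Considerations is two sentences long. The first names the only test in the document: "A two tailed paired t-test will be utilized to evaluate a clinically significant difference of 2 hours between the two groups". The second gives the sample size: "Each group will contain 47 participants in order to achieve a power of 0.9 and Alpha of 0.05". Neither sentence gives a standard deviation, an SD of differences, a within-pair correlation or a source for the variability.

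Study Procedures, item 2 (Comparison Groups) describes who is compared. The total is 94 children: "We will collect data on 94 subjects having a GU procedure and caudal as standard of care". One group is caudal only: "We will collect information on 47 subjects who receive caudal only". The other is made up of further children: "We will collect information on an additional 47 subjects who receive a caudal and IV dexamethasone". Item 1 of the same section gives the design as follows: "Study design: prospective data collection".

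Group membership is decided in routine care. Under Risks to patient/ adverse event response the protocol says: "IV dexamethasone will be given at the discretion of the anesthesiologist". No section describes a crossover, a repeated measurement, matching variables or any other rule that would form pairs.

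**The concern.** A paired t-test works on within-pair differences. It needs a one-to-one link between observations: the same child measured twice, or two children matched by a stated rule. Here each child contributes to one group only, and nothing links the groups.

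An analyst who follows the text must therefore invent the pairs, most simply by lining up the rows of two data columns. The mean difference does not change with that order, but its standard error does, and so does the p-value. The one planned test would then not be a unique function of the data. A result near 0.05 could be called significant or not according to how the file was sorted. If the row links are kept, a missing value in one group also discards an unrelated child from the other.

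The sample-size sentence raises a separate and lesser point. Without an SD, a reader cannot verify the power of 0.9 or tell which test it was calculated for.

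**Working it through.** **Inputs from the protocol.** Difference 2 h, two-sided alpha 0.05, power 0.9 and 47 per group (Statistical Considerations); 94 separate children (Study Procedures, item 2). The SD and the rate of missing data are not given, so values used for them below are assumptions.

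**1. Reproducing the stated 47.** Without an SD, 47 cannot be derived forwards. It can be solved backwards for the SD that gives power 0.9, using the noncentral t distribution.

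- Independent groups (92 df, critical t 1.986): noncentrality = 2 / (SD × √(2/47)). Power is 0.90 at SD = 2.96 h, where the noncentrality is 2 / (2.96 × 0.2063) = 3.28.
- Paired (46 df, critical t 2.013): noncentrality = 2 / (SD of differences / √47). Power is 0.90 at an SD of differences of 4.141 h, where the noncentrality is 2 / (4.141 / 6.856) = 3.31.
- For unrelated children, the SD of differences is √2 times the per-child SD, so 4.141 / √2 = 2.928 h per child. Two-sample power at that SD is 0.906.

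The two readings imply nearly the same per-child SD (2.96 and 2.93 h). The figure 47 therefore does not reveal which test was planned, and it is consistent with an independent-groups calculation.

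**2. Why row order matters.** Let r be the sample correlation that a given row order happens to create. With equal group SDs,

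paired t = independent-groups t / √(1 − r).

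Under random ordering, r has mean 0 and SD 1/√46 = 0.147, so about 95% of orderings give r between −0.29 and 0.29. Take data with an independent-groups p of exactly 0.05, that is t = 1.986:

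- r = 0.29: 1.986 / √0.71 = 2.357, p = 0.023 on 46 df.
- r = −0.29: 1.986 / √1.29 = 1.749, p = 0.087.
- p < 0.05 requires r > 1 − (1.986/2.013)² ≈ 0.026, or 0.026 / 0.147 ≈ 0.18 SD above zero. The probability is about 43%.

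Simulation agrees. Over 200 normal data sets with 2,000 orderings each, the central 95% range of p was 0.023 to 0.087, and 43% of orderings were below 0.05 (40% to 47% across data sets).

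Away from 0.05 the effect fades. One simulated data set was shifted to other p-values and re-paired 20,000 times at each:

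| Independent-groups p | Share of pairings with p < 0.05 |
|---|---|
| 0.01 | 100% |
| 0.02 | 99.7% |
| 0.03 | 91% |
| 0.04 | 69% |
| 0.06 | 24% |
| 0.08 | 6% |
| 0.10 | 1.5% |
| 0.15 | about 0% |

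**3. Averaged over all data sets** (assumed SD 2.96 h, 400,000 simulated data sets). Type I error is 0.050 under either test. An arbitrary pairing and the two-sample t-test disagree at the 0.05 level in 1.3% of data sets with no true difference, 4.4% with a true 1 h and 2.2% with a true 2 h.

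**4. Power at 47 per group for a true 2 h.**

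| Assumed per-child SD | Two-sample t | Paired, arbitrary pairs | n per group for 0.90, two-sample |
|---|---|---|---|
| 2.96 h | 0.900 | 0.894 | 47 |
| 3.5 h | 0.783 | 0.774 | 66 |
| 4 h | 0.669 | 0.660 | 86 |
| 5 h | 0.484 | 0.476 | 133 |

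The fall down each column comes from the assumed SD. The cost of pairing is the gap across each row, always below 0.01.

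**5. Missing values** (assumed 10% per group, SD 2.96 h). With fixed row links, 47 × 0.9 × 0.9 ≈ 38 pairs remain, and power is 0.82, against 0.86 for a two-sample test on 42 per group. If the available children are re-paired, it is 0.856 against 0.864.

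**The case against.** The strongest objection is that this is a slip of one word. The surrounding language, two groups with 47 participants in each, is that of an independent comparison, and an analyst would notice that no pair identifier exists. That may be so, but the documents cannot settle it. Nothing elsewhere corrects the word, and a plan should not depend on the analyst overriding it.

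A second objection is that little is lost on average, and this stands. With complete data the estimated difference is the same under either test, type I error holds and power drops by less than 0.01. The 43% figure applies only to data sets that sit exactly at p = 0.05; across all data sets the disagreement is 1.3% to 4.4%. One qualification is that these averages assume a row order unrelated to outcome, which the plan does not secure. In one simulated example with a two-sample p of 0.052, sorting both columns the same way gave a paired p of about 2 × 10⁻¹¹, and sorting them in opposite directions gave 0.16. That is an extreme case, not a prediction.

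Third, the missing SD is a reporting gap and not evidence of an underpowered study. That is correct, and it adds no weight to the main point. The 10% missing rate is likewise only an assumption; entry is limited to inpatients and follow-up ends at 24 hours.

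Finally, the statistical section does not name the outcome measured in hours. If it is the time to first analgesic dose, children who need none within 24 hours have no observed time, and a t-test of either kind does not handle that. This is a fair but separate issue, and it does not rescue the paired test.

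**Conclusion.** The concern holds. The only test named in the plan requires pairs, and the design supplies none. The consequence is a p-value that is not fixed by the data. It matters when an independent-groups p would fall between roughly 0.02 and 0.10, and it is negligible elsewhere. Average type I error and power are essentially unaffected as long as row order is unrelated to outcome. These sizes assume normal outcomes with equal SDs, and the overall disagreement rates also assume a per-child SD of 2.96 h.

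The stated power of 0.9 is uncheckable, not shown to be wrong: it is correct for an independent-groups test if the per-child SD is about 2.96 h. The larger sample sizes at other SDs show sensitivity to an unstated input, not a demonstrated shortfall. The mismatch should be corrected before analysis because it affects the sole planned test and costs almost nothing to repair.

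**What to change.** Replace the paired t-test with an independent two-group comparison, for example a Welch two-sample t-test, and report the difference with its 95% CI. If pairing really was intended, state the matching variables and tolerances, fix them before outcomes are seen, and give the sample size in pairs. In either case, state the assumed per-child SD and where it comes from. For the independent-groups test, restate the power of 47 per group at that SD.

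The cost is two or three sentences of protocol text and no new data items. The restated power may be less favourable, since 47 per group reaches 0.90 only up to an SD of about 2.96 h. A matching rule would lose the children who cannot be matched. Changing the test also does not adjust for differences between children whose anesthesiologist chose dexamethasone and those whose anesthesiologist did not.

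### The plan has no rule for a child with no analgesic dose by the end of follow-up; leaving such children out would restrict the comparison by outcome, by an unknown amount

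*Combined protocol and SAP*

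**What the plan says.** Statistical Considerations contains two sentences. The first gives the analysis: "A two tailed paired t-test will be utilized to evaluate a clinically significant difference of 2 hours between the two groups". The second gives the size: "Each group will contain 47 participants in order to achieve a power of 0.9 and Alpha of 0.05". Neither names an end-point, an SD or an undosed share.

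Study Procedures 3d lists "Time to first analgesic dose" as item iv, without a time origin, an end, or a value for a child who gets no dose. Item vi is "Amount of pain medicine received during floor stay", and the time of the caudal is also recorded.

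Follow up/Record Retention sets the window: "The participation in the study begins with induction of anesthesia and ends after the 24 hour follow up". It does not say when the 24 hours start. Study Procedures 3c adds: "The patient will have a final pain evaluation by the Acute Pain Service attending the day following caudal placement".

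Subject Withdrawal says that on withdrawal "data already collected will be kept and utilized, but no more data for the study will be collected". That covers children who withdraw, not those who complete follow-up undosed, and it does not say how an incomplete time enters the test.

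**The concern.** A t-test needs one number per child. A child still undosed when observation stops supplies only the statement that the time exceeds some value. The analyst must then drop the child, enter the cutoff as if it were a dose time, or censor. The plan does not choose.

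The treatment is meant to lengthen analgesia, so an undosed child may be its clearest success. Dropping such children conditions on an outcome that treatment may change, and the comparison then covers only children who needed a drug. A benefit consisting of more children needing no dose would be missed by the one stated test. With no rule in place, the handling can also be chosen after the data are seen.

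Entering 24 h is sound for a child followed for 24 h from the chosen origin. It is not sound for a child who leaves undosed earlier.

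**Working it through.** **Inputs from the protocol.** 47 per group, difference 2 h, two-sided alpha 0.05, power 0.9, a 24-hour follow-up.

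**Inputs assumed.** The SD, the undosed shares, and a mean of 8 h for dosed control children unless stated. None of these is in the documents.

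**1. The plan's own figure.** Without an SD, 47 cannot be reproduced, only solved backwards. Treating the groups as independent, SD = 2 × √(47/2) / (1.960 + 1.282) = 2.99 h by the normal approximation, or 2.96 h with the t distribution. Read as 47 pairs, the SD of the difference is 4.14 h (t-based). I use 2.96 h.

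**2. Can ordinary variation carry children past 24 h?** With normal times and SD 2.96 h, P(T > 24) = 1 − Φ((24 − mean)/2.96):

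| Mean (h) | P(T > 24 h) |
|---|---|
| 10 | 1.1 in a million |
| 16 | 0.3% |
| 20 | 8.8% |

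Unless mean times are near 20 h, the problem arises only if some children never need a dose.

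**3. Undosed status unrelated to timing, 10% v 30% undosed, equal timing among the dosed.**
- Left out: 8 − 8 = 0.0 h, power 0.05.
- Counted to 24 h: control 0.9 × 8 + 0.1 × 24 = 9.6 h; dexamethasone 0.7 × 8 + 0.3 × 24 = 12.8 h; difference 3.2 h. Simulated power is 0.63 with the Kaplan-Meier restricted mean and 0.62 with a t-test on capped times.
- With 10% v 20% the counted difference is 0.1 × 16 = 1.6 h, power 0.23.
- For dosed means of 4, 8, 12 and 16 h, the counted 10% v 30% difference is 0.2 × (24 − mean) = 4.0, 3.2, 2.4 and 1.6 h.

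**4. The undosed are those who would have been dosed latest, 10% v 30%, otherwise equal timing.** The mean of the remaining children is 8 − 2.96 × φ(z)/(1 − p).
- Control: 8 − 2.96 × 0.1755/0.9 = 7.42 h.
- Dexamethasone: 8 − 2.96 × 0.3477/0.7 = 6.53 h.
- Left out: 6.53 − 7.42 = −0.9 h.
- Counted: (0.7 × 6.53 + 0.3 × 24) − (0.9 × 7.42 + 0.1 × 24) = 11.77 − 9.08 = +2.7 h.

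Here leaving out reverses the sign.

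**5. One normal distribution cut off at the end of follow-up, true shift 2 h.** With 1%, 5%, 10% and 20% of caudal-only children undosed, leaving out shrinks 2 h to 1.76, 1.44, 1.23 and 0.98 h, with power 0.86, 0.75, 0.64 and 0.47. For a 24 h cutoff this needs long times: 10% undosed implies a control mean of 24 − 1.2816 × 2.96 = 20.2 h.

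**6. Equal undosed shares, 2 h shift among the dosed (SD 2.96 h for dosed children).**

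| Undosed, each group | Power, left out | Power, restricted mean |
|---|---|---|
| 0% | 0.91 | 0.91 |
| 2% | 0.89 | 0.76 |
| 5% | 0.88 | 0.57 |
| 10% | 0.87 | 0.39 |

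At 10% the estimates are 2.0 h (left out) and 0.9 × 2 = 1.8 h (counted).

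**7. If 2.96 h is instead the SD of all children counted to 24 h.** Then p(1 − p)(24 − m)² cannot exceed 2.96² = 8.76. For dosed means m of 4, 8, 10 and 12 h, the undosed share p is at most 2.2%, 3.5%, 4.7% and 6.5%, about 1 to 3 of 47.

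**8. Withdrawal alone.** With an assumed 10% leaving between 0.5 and 8 h and a 2 h shift, leaving out gives 2.03 h and the restricted mean 2.00 h.

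Simulated powers rest on 5,000 trials per scenario, Monte Carlo SE at most 0.007.

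**The case against.** The strongest reply is that the harm is hypothetical. A reader might infer that the investigators intend to drop undosed children. The documents do not support that: they are silent, and the withdrawal rule, which keeps data already collected, leans the other way.

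The text also points to few undosed children. The Introduction calls the limited duration of single-shot local anesthetic a major drawback, surgery is inpatient, and "All patients will have their pain orders written by the anesthesia acute pain service and pain scores monitored per hospital protocol". Under step 7 the 10% v 30% example is impossible at dosed means of 4 to 12 h. All of this stands as a limit on size; none of it supplies the missing rule.

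The end-point is inferred, and item iv carries no 24-hour limit of its own. Drug amounts in PACU and on the floor would show undosed children as zero, so a no-dose benefit would not be wholly invisible, although no test is stated for those items. These points stand.

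A reader might also infer that leaving out only ever weakens the result and keeps its sign. Step 4 shows otherwise. Nor does it always cost power: in step 6 it has more power than counting.

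Finally, the restricted mean is one choice among several. With equal shares of 5% and 10%, a Wilcoxon test with undosed children set at 24 h has power of about 0.81 and 0.7, better than 0.57 and 0.39. In the 10% v 30% equal-timing case it has about 0.39 against 0.63. Neither dominates, which is a reason to choose beforehand. The 24 hours may also run from induction, which precedes the caudal; a horizon of 24 h from caudal would then lie beyond what is observed.

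**Conclusion.** The gap is certain; its size is not. The plan pairs an end-point that some children may not reach with a test that needs an observed value for each, and gives no rule. If undosed children are left out, the result depends on who they are: in the assumed scenarios the estimate is unchanged at 2.0 h, shrinks (2 h to 1.23 h), vanishes (0.0 h against 3.2 h counted), or reverses (−0.9 h against +2.7 h counted). If every child is dosed within the window, nothing changes.

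This rests on the 2-hour difference referring to time to first analgesic dose, on assumed undosed shares, and in most examples on an SD solved back from 47. It supports a correction that should be made before analysis, with medium confidence that it matters in practice. It does not support a claim that the trial's result will be biased.

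**What to change.** Before analysis, add a short paragraph that:

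- names time to first analgesic dose as the end-point of the 2-hour comparison and states its time origin and when the 24 hours start;
- keeps every child, and censors an undosed child at the end of observed follow-up, or at withdrawal if earlier;
- compares the two groups unpaired with a method that accepts censoring, for example the Kaplan-Meier restricted mean difference with a 95% CI, to a horizon inside every completer's observed follow-up;
- reports the undosed count in each group;
- describes the power of 0.9 as conditional on almost no censoring, and states the undosed share assumed.

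The restricted mean keeps the scale in hours and equals the difference in means capped at the horizon when nobody leaves early.

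The cost is a few sentences and a standard analysis. The time of the caudal, the time to first dose and drug amounts are already collected. No power is lost if every child is dosed. The real downside is the loss in step 6 when undosed shares are similar in the two groups. If that pattern is thought likely, a rank test that keeps every child could be specified instead, accepting its lower power when the groups differ mainly in the undosed share.
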